University of Miami - Miller School of Medicine

Set-Enhanced Aftercare for Mothers in Substance Abuse Recovery and Their Children

Version Date 6-7-2016

National Clinical Trial Number: NCT02702193

[name]

4. Description of Study

Study Protocol

4.1. * Abstract and Specific Aims

Include a brief summary of the significance, purpose or research question, specific aims, and risks/benefits. Specific aims include hypotheses you will investigate.

The study will conduct a translational randomized trial comparing an adaptation of Structural Ecosystems Therapy (SET), "Healthy Home", as an enhancement of substance abuse or mental health outpatient treatment, to outpatient treatment as usual (TAU) among approximately 172 Black, Hispanic and White non-Hispanic mothers enrolled in outpatient substance abuse, mental health or substance abuse as a co-occurring condition treatment. The study will be conducted with a community partner, Banyan Health Systems (also known as Miami Behavioral Health and Spectrum Programs), that delivers integrated substance abuse/mental health treatment and primary care. Agency staff will conduct data collection and agency nurses will deliver Healthy Home. Data will be collected at baseline and 4, 8, and 12 months post-randomization.

The Specific Aims of the proposed study are to:

- 1) test the effectiveness of SET for improving physical and mental health and reducing relapse of mothers in substance abuse/mental health recovery;
- 2) test the effectiveness of SET for improving health and mental health outcomes of children of mothers in recovery;
- 3) test mechanisms of action of SET (self care, environmental risk, family functioning and stigma);
- 4) assess SET implementation and sustainability factors and the relationship between fidelity and outcomes; and
- 5) examine the interactions of ethnicity and ethnicity-related factors on outcomes.

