QA monitoring will be conducted by staff of El Centro according to the standard procedures which include a QA review prior to initiation, upon conducting baseline procedures with the

first few study participants, and then for interim reviews.

4.12. * Support the study validity by describing the statistical design, including quantitative and qualitative methods used to analyze data.

The following is the planned data analysis procedure as submitted in the grant application.

-Testing of data quality and distributional assumptions.

Distributions and frequencies of all measures will be examined for non-normality and transformed as needed. If transformation is not sufficient, other distributions (Poisson, Negative Binomial) or nonparametric analyses will be used. Internal consistency will be reported for all measures with Cronbach's alpha. If any scale alphas are below .70, item total correlations and/or factor analysis will be employed to diagnose the psychometric problems and new scales with higher internal consistency will be considered.

-Evaluating the effectiveness of randomization will be accomplished by use of ANOVA and Chi-square of baseline variables. Although not anticipated, if variables with theoretical importance to outcomes show baseline differences by condition, hypotheses tests will statistically control for (baseline) differences.

-Growth curve analysis. Latent growth modeling (LGM) in Mplus 6 (Muthén & Muthén, 2010) will examine change over time in the outcomes. LGM involves creating latent variables representing growth parameters (the baseline or intercept; the linear slope or rate of change, the quadratic slope, etc.). It allows for the simultaneous estimation of multiple growth functions with growth parameters of one function related to growth parameters of another. Mplus allows for outcome variables with distributions that are not continuous (e.g., Poisson for skewed variables or logistic for binary outcomes), which is particularly important with substance use and health outcomes. LGM can generate effect sizes for rate of change or the difference at a single time between the two conditions, i.e., Cohen's d (Cohen, 1992). Following Cohen's (1992) guidelines, we will interpret our effect sizes using the convention of "small" ($d = .2$), "medium" ($d = .5$), and "large" ($d = .8$).

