-Testing hypothesized differences between experimental and control groups will use an intent-to-treat analysis that includes all participants randomized. LGM will examine the effect of treatment condition on trajectories of change separately for each of the outcomes over the one-year follow-up. To test Hypothesis 1, we will assess the trajectories of the mothers' outcomes (mental health, physical health, substance abuse, etc.) and predict of the trajectory of change by intervention condition (Healthy Home vs. TAU). Controlling for the effects of socio-demographic variables and pretest levels of the dependent variables is possible in LGM, if these variables are found to differ by randomization group. To test Hypothesis 2, a similar procedure will consider children's outcomes (mental health, physical health, behavior problems, etc.).

- Testing mechanisms of action. Using Mplus 6, this set of analyses will investigate links between trajectories of change (growth curves) for the hypothesized mechanism of action variables (mediators) and trajectories of mothers' outcomes or children's outcomes following MacKinnon, Lockwood, Hoffman, West and Sheets' (2002) procedures. This method is more powerful than the classic (Baron & Kenny, 1986) method, particularly for binary outcomes. LGM can also test multiple indirect paths or mediators (i.e., Hypothesis 3c) with this method.

- Clinically significant change procedures (Jacobson & Traux, 1991) can also investigate efficacy of an intervention. These procedures: 1) determining whether participants have made statistically reliable change and 2) categorizing subjects according to clinically meaningful cut-points, e.g., recovered (statistically reliable change that moves a client out of clinical range), improved (statistically reliable improvement, but still in the clinical range), and unimproved/deteriorated.

-Implementation analysis will be used to determine the feasibility of adapting Healthy Home for other agencies. Using cost logs for training and service delivery, the total cost of

implementing Healthy Home can be determined. Therapist and agency satisfaction as well as therapist fidelity to Healthy Home will be assessed to determine if changes to the Healthy Home implementation protocol are needed.

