-Mothers will have additional data from baseline assessments administered by the treatment agency: a GAIN-I administered at treatment intake and a GAIN-M90 administered 90 days into treatment. As noted in the measures section, several variables (e.g., demographics, history of abuse) will be taken from the GAIN-I. There are a number of follow-up analyses that may provide greater understanding of the direct and interactive relationships between symptoms, intervention, and post-treatment substance use, including adding to growth models of mental or physical health and examining moderators of treatment effects. [The GAIN is no longer being used in the study]

- Proposed moderators will be used in two types of analyses. The variables might predict trajectories of change of the mothers' and children's outcomes, only. For example, does poor sleep contribute to early relapse for mothers in recovery? The moderators might also interact with treatment. For example, do mothers from different ethnic groups respond differently to Healthy Home? Effect sizes will be generated for future intervention development/refinement from the results of these exploratory analyses.

- Secondary data analysis will be used to examine data extracted from clinical intervention forms related to health assessments, recommendations/referrals, treatment/services rendered, follow-up plan of care, and education provided to individuals during home health visits.

- Missing data and attrition patterns will be examined. In research with samples of individuals in substance use recovery some loss to follow-up is expected. Our proposed methods allow the inclusion of cases with randomly missing data, we will test for non-randomness, i.e., a non-ignorable or informative missing data pattern (Little & Rubin, 1987). If there is differential attrition by condition, alternative models will be examined (in addition to the proposed) which account for or model the attrition mechanism (Angrist, 1997; Heckman, 1979; Idson & Feaster, 1990) to produce a more robust range of estimates.

Privacy/Confidentiality Agreements

4.13. **Describe any privacy agreements or certificates of confidentiality, if applicable.**
We have received a certificate of confidentiality from NIH.

4d. Description of Study (cont'd)

Deception

4.14. *** Is the use of deception part of the study design?**

Yes No

If yes, please answer the following 3 questions:

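### Aim 3 names no covariates for its mediation models, and the plan's one general adjustment rule, imbalance by arm, does not address mediator-outcome confounding

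*Combined protocol and SAP*

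**What the plan says.** Section 4.1 makes mechanisms a specific aim: "test mechanisms of action of SET (self care, environmental risk, family functioning and stigma"). The trial has "approximately 172 Black, Hispanic and White non-Hispanic mothers", and "Data will be collected at baseline and 4, 8, and 12 months post-randomization".

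Four places in section 4.12 bear on covariates:

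- *Evaluating the effectiveness of randomization*: the check "will be accomplished by use of ANOVA and Chi-square of baseline variables". The consequence is that "if variables with theoretical importance to outcomes show baseline differences by condition, hypotheses tests will statistically control for (baseline) differences". No threshold is given.
- *Testing hypothesized differences*, in the Hypothesis 1 text: control for socio-demographic variables and pretest levels "is possible in LGM, if these variables are found to differ by randomization group".
- *Testing mechanisms of action*: the models "investigate links between trajectories of change (growth curves) for the hypothesized mechanism of action variables (mediators) and trajectories of" mothers' or children's outcomes. The paragraph names no covariates, no assumption about confounding and no sensitivity analysis.
- *Proposed moderators*: "The variables might predict trajectories of change" in the outcomes, or they may interact with treatment. Both uses are exploratory, and neither is tied to the mediation models.

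Section 4.4 lists the moderator measures: ethnicity, socio-economic status, household composition, mother's stress, abuse history and sleep.

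**The concern.** A mediation claim needs two links: arm to mediator, and mediator to outcome given arm. Randomisation protects the first. It does not protect the second, because mothers are not randomised to values of self-care, family functioning or stigma. If a baseline characteristic makes both the mediator and the outcome improve faster, the two trajectories will be associated although neither acts on the other.

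Balance between arms says nothing about this. A variable with identical arm means can still confound the mediator-to-outcome path, and when randomisation works the by-arm rule will rarely bring that variable into the model. If Healthy Home then truly shifts the mediator, both links can be significant and Aim 3 would report a mechanism that does not exist. That would misdirect later refinement of the intervention.

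**Working it through.** The documents give no alpha, power, planning effect size or confounder strength, so there is no figure to reproduce. The check shows how often mediation would be declared when the mediator does nothing.

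**From the documents.** N = 172 (section 4.1); adjustment only for variables that differ by arm (section 4.12).

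**Assumed.** 1:1 allocation; two-sided 0.05 for each test, including the by-arm check; mediation declared when both links are significant; one baseline variable U, independent of arm, correlated r with the mediator slope and with the outcome slope within arm; arm effect d on the mediator slope in within-arm SD units; true mediator-to-outcome effect zero.

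**Step 1: bias.** Within arm, the covariance of the two slopes is r × r and the mediator variance is 1. The unadjusted mediator-to-outcome coefficient is therefore r² when the truth is 0: 0.09, 0.25 and 0.49 for r = 0.3, 0.5 and 0.7. Simulation gave averages of 0.09, 0.25 and 0.49.

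**Step 2: mediator-to-outcome test.** z = r² × √(172 − 3) / √(1 − r⁴), with √169 = 13.
- r = 0.2: z = 0.52, significant in 8%.
- r = 0.3: z = 1.17, significant in 22%.
- r = 0.4: z = 2.11, significant in 56%.
- r = 0.5: z = 3.36, significant in 92%.

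**Step 3: arm-to-mediator test.** With 86 per arm, power is about 0.90 at d = 0.5, 0.50 at d = 0.3 and 0.26 at d = 0.2.

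**Step 4: both links under the by-arm rule.** U is balanced in expectation, so the check triggers adjustment in about 5% of trials. The false-mediation rate is 0.95 × (step 2 × step 3) + 0.05 × (0.05 × step 3). For r = 0.5, d = 0.5: 0.95 × 0.919 × 0.903 + 0.05 × 0.05 × 0.903 = 0.79.

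| d | r | Formula | Simulated | Always adjusted |
|---|---|---|---|---|
| 0.2 | 0.2 | 2% | 2% | about 2% or less |
| 0.2 | 0.3 | 5% | 4–6% | about 2% |
| 0.3 | 0.3 | 10% | 10% | about 3% |
| 0.3 | 0.5 | 44% | 42–43% | about 3% |
| 0.5 | 0.2 | 7% | 7–8% | about 5% |
| 0.5 | 0.3 | 19% | 17–20% | about 5% |
| 0.5 | 0.4 | 48% | 47–49% | about 5% |
| 0.5 | 0.5 | 79% | 78–80% | about 5% |

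Ranges are across repeated sets of simulated trials. Never adjusting gave almost the same result as the by-arm rule (83% against 80% at d = 0.5, r = 0.5).

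**Step 5: conditions that change the answer.**
- *Slope reliability 0.6, d = 0.5.* The slope correlation falls to 0.6 × r² and d to 0.5 × √0.6 = 0.39. Rates are about 7%, 17% and 34% for r = 0.3, 0.4 and 0.5.
- *Healthy Home does not move the mediator (d = 0).* At or below about 4%.
- *U affects levels but not change.* About 4% in a four-wave simulation.
- *About 20% lost (172 × 0.8 ≈ 138), d = 0.5.* 13% and 67% for r = 0.3 and 0.5.
- *Only the observed baseline mediator and outcome added, four waves, d = 0.5.* 17% and 60% for r = 0.3 and 0.5, against 11% and 52% with no adjustment and about 4% with U adjusted for. Baseline values alone do not remove the bias.
- *U measured with reliability 0.7, always adjusted, d = 0.5.* 10% and 20% for r = 0.4 and 0.5.

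**The case against.** A reader might infer that the plan prescribes by-arm adjustment for Aim 3. It does not say so: the mechanisms paragraph is silent, and the rule reaches it only through the general reference to hypothesis tests. Nor does that rule forbid other covariates. Section 4.12 describes itself as the procedure submitted in the grant application, and it cites a Hypothesis 3c that it never lists, so more detail may exist elsewhere. This stands, and the point is therefore an omission plus a general rule that would not fill it. Nothing else in the documents handles mediator-outcome confounding.

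A reader might also infer that the plan itself expects such confounders. The moderator paragraph says only that moderators may predict outcome trajectories. Its predictor example is sleep, and it does not name stress, abuse, socio-economic status or household. It says nothing about predicting mediators, and confounding needs both links. Shared causes are plausible here, but the documents do not assert them.

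Finally, the large rates need a sizeable shift in the mediator and a variable fairly strongly related to both slopes. With weak confounding or noisy slopes the error is close to nominal. That also stands, and is why the size is given as a range.

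**Conclusion.** The concern holds as an omission that should be corrected. The plan names no covariates for the mediation models, and its only general criterion screens on a property unrelated to confounding of the mediator-to-outcome path.

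If the by-arm rule is followed, the risk of a false mechanism runs from negligible to about 80%, depending on r, d and slope reliability. All three are assumptions. It arises only when Healthy Home moves the mediator and a baseline variable drives change in both mediator and outcome. The first condition is also the situation in which a mechanism would be claimed.

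It would be wrong to infer that the main results are affected. Leaving out balanced covariates does not bias the Aim 1 and 2 arm comparisons. It would also be wrong to treat the roughly 5% under adjustment as guaranteed: that figure assumes one known confounder, measured without error.

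**What to change.** Add to section 4.12, *Testing mechanisms of action*:

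> In every mediation model, the mediator slope and the outcome slope are both regressed on the same pre-specified baseline covariates, whether or not these differ by condition: baseline mediator and outcome (the growth intercepts), ethnicity, socio-economic status, stress, abuse history, sleep and household composition. Only baseline values are used. The indirect effect is also reported over a stated range of assumed residual correlations between mediator and outcome.

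The sensitivity analysis is needed because adjustment removes only measured confounding, and does so imperfectly when covariates carry measurement error. The documents offer no basis for its range, so the investigators should choose and justify one in advance.

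The covariates come from the section 4.4 measures, assuming the moderator measures are taken at baseline, so no new data collection is needed. The cost is in model size. Six covariates on two slopes add 12 paths, or 14 if ethnicity takes two indicators; two intercepts on two slopes bring this to 14 + 4 = 18. Putting the six covariates on the intercepts as well would give 6 × 2 × 2 = 24 covariate paths before the ethnicity indicators. At about 172 mothers this costs a little precision and may strain convergence. The plan can say in advance that covariates will be limited to the slopes, or combined into one baseline score, if a model does not converge.

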A table listing each construct, instrument and translation information is attached. Most of the measures have Spanish versions – either published or used in previous protocols, if not they will be translated using translation/back-translation methods. The following measures are planned to be used with mothers and children. No additional instruments or measures will be used without seeking IRB approval.

Mother Outcome Measures

- Mental Health will be assessed using the Hospital Anxiety and Depression Scale (Zigmond & Snaith, 1983).
- Physical Health will be assessed using the PROMIS Global Health Scale (Hays, Bjorner, Revicki, Spritzer, & Cella, 2009). Clinical measurement of height and weight (i.e., body mass index) and waist circumference will be indicators of obesity.
- Dental Health will be assessed using the Oral Health Impact Profile short form (OHIP-14) (Slade, 1997).
- Substance Use will be assessed using the Addiction Severity Index Lite Alcohol and Drug Scale (McGahan, Griffith, Parente, McLellan, 1986), and a urine drug toxicology test.

Child Outcome Measures

- Mental health will be assessed using the Youth Self-Report (Achenbach & Rescorla, 2001) and Child Behavior Checklist (CBCL; Achenbach, 2009).
- Physical Health will be assessed with the Child Health Questionnaire (Landgraf & Abetz, 1997). Additionally, height and weight will be obtained to calculate BMI. No urine or blood samples will be taken from children.
- Dental Health will be assessed using the Oral Health Impact Profile-14 (Slade, 1997) and three items from the Florida Dental Health Survey (Gilbert & Litaker, 2007).

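### Attrition-mechanism models are required only if attrition differs by condition, so under balanced loss the maternal substance-use results need no missing-not-at-random sensitivity analysis

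*Combined protocol and SAP*

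**What the plan says.** Section 4.12 holds the only missing-data rule in the document. It starts from the expectation of loss ("In research with samples of individuals in substance use recovery some loss to follow-up is expected") and then makes three statements.

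- On the main analysis: "Our proposed methods allow the inclusion of cases with randomly missing data".
- On checking that assumption: "we will test for non-randomness, i.e., a non-ignorable or informative missing data pattern". No method, threshold or consequence is given.
- On alternatives: "If there is differential attrition by condition, alternative models will be examined". These are to be run in addition to the proposed models, and are described as models "which account for or model the attrition mechanism".

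Elsewhere in 4.12, the test of the treatment conditions "will use an intent-to-treat analysis that includes all participants randomized", by latent growth models fitted to each outcome. The software is said to allow non-continuous outcomes, including "logistic for binary outcomes". Under Mother Outcome Measures in 4.4, "Substance Use will be assessed using the Addiction Severity Index Lite Alcohol and Drug Scale", together with a urine toxicology test. There is no rule for a missing interview or urine sample.

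**The concern.** The trigger looks at the wrong thing. How many mothers are lost in each arm says little about whether loss is related to the outcome. If mothers who are using substances are more likely to disappear from one arm than from the other, the two dropout percentages can be equal while a growth model that assumes missing at random gives a biased comparison. In that case the written rule calls for nothing further. The promised test does not fill the gap, because distinguishing ignorable from non-ignorable missingness depends on the values that were not seen.

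Substance use is where this matters most. Reducing relapse is part of Aim 1 (4.1), and outcome-related loss is plausible: 5.4.A.(i) suspends study procedures during incarceration, although they may resume on release within the visit window. Phone assessments (4.4) are a smaller problem. They can still yield the self-reported Addiction Severity Index and lose only the urine sample and body measurements. What is at stake is whether a reader can see how far the substance-use result, presented as intent-to-treat on all randomized mothers, rests on missing at random.

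**Working it through.** **The logic of the rule.** The plan states no attrition rate, significance level or power figure, so there is no figure of its own to reproduce. The text can be laid out by case:

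| Attrition | Non-ignorability test | Attrition-mechanism models |
|---|---|---|
| Differs by condition | promised, no consequence | required |
| Balanced | promised, no consequence | not required |

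**Inputs for an illustration.** From the documents: about 172 mothers and four visits (baseline, 4, 8 and 12 months). Everything else is assumed: 1:1 allocation (172/2 = 86 per arm), no true effect, equal loss of 15%, 25% or 35% in both arms, and two-sided 5% tests.

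**Binary outcome (such as a positive urine), 30% positive at 12 months.**

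- Data: logit P = b0 + random intercept (SD 1.5) + random slope (SD 0.4 per visit), the same in both arms.
- Dropout at visits 2 to 4, without return: logit hazard = a + g × (current unseen value). Here exp(g) is the dropout odds ratio for a positive mother, and a is set in each arm to give the stated loss.
- Fit: maximum-likelihood logistic growth model with a common intercept and arm-specific slopes, on exact expected cell frequencies, so there is no simulation error.

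False 12-month risk difference, in percentage points:

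| Dropout odds ratio by arm | 15% lost | 25% lost | 35% lost |
|---|---|---|---|
| 3 and 3 | 0 | 0 | 0 |
| 3 and 1.73 | 1.0 | 1.7 | 2.5 |
| 3 and 1 | 1.9 | 3.3 | 4.8 |
| Standard error (3 and 1), 86 per arm | 6.6 | 6.8 | 7.2 |

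The sign reverses if the arms are exchanged. With 20% to 40% positive, the 3-and-1 row becomes 1.6–2.0, 2.8–3.4 and 4.0–5.1. Replacing 3 by 2 or 5 and varying the random-effect SDs from 1.0/0.3 to 2.5/0.6 gives 1.1–2.9, 1.8–5.0 and 2.7–7.2.

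**Effect on the error rate.** With z = bias / standard error, the rejection rate is 1 − Φ(1.96 − z) + Φ(−1.96 − z). For 3 and 1:

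- 15% lost: z = 1.91/6.55 = 0.29, rate 6.0%
- 25% lost: z = 3.31/6.84 = 0.48, rate 7.7%
- 35% lost: z = 4.83/7.17 = 0.67, rate 10.3%

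For 3 and 1.73, the rate is about 5% to 6.5%.

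**Continuous outcome (such as a severity score).** Assumptions: intercept variance 0.5, slope variance 0.03, residual variance 0.4, and generalized least squares with known variances. If the log-odds of dropout rise by 1 per SD in one arm only, the false difference is about 0.06/0.09/0.14 SD, against standard errors of 0.14/0.14/0.15 SD. With 1 in one arm and 0.5 in the other it is about 0.03/0.04/0.06 SD. With the same link in both arms it is about 0.

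**Sensitivity of the trigger (a side point).** The plan does not say how differential attrition would be judged. If it were a 5% Pearson chi-square test at 86 per arm, exact power to detect 20% versus 30% loss would be 33%. So a real imbalance of 10 points would usually not trigger the models either.

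**The case against.** The strongest reply is that the plan already takes informative missingness seriously. It expects loss, promises to examine attrition patterns, promises a test for a non-ignorable pattern whatever the balance, and cites models of the attrition mechanism. A reader might infer from this point that the plan has no check at all for data missing not at random. The text does not support that: a test is promised unconditionally. What is missing is a required sensitivity analysis when attrition is balanced.

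It can also be said that differential attrition is undefined and could cover who leaves as well as how many. The wording does not say so. Even on that reading, the trigger could respond only to differences visible in observed data, and would miss dropout that depends on unseen outcomes.

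Three parts of the opposing case stand.

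- Bias in the comparison needs an arm-specific link between outcome and dropout. The documents show none, and the incarceration rule applies equally to both arms.
- Retention measures lower the risk: monthly calls, home-based assessments, a final-assessment window extending to 18 months (all in 4.4) and $50 per assessment (6.5.A). They do not exclude informative loss.
- The illustrated biases are modest.

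A simpler calculation would look more alarming. Suppose 40% relapse in both arms, 30% are lost from each, and those lost relapse at 80% in one arm and 40% in the other. Completers in the first arm then show (0.40 − 0.30 × 0.80)/0.70 = 22.9%, a false gap of 17.1 points. That compares completers at a single time point. The planned growth model also uses the earlier visits of mothers later lost, so this figure should not be used to judge the plan.

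**Conclusion.** The point holds as a cheap improvement. Under balanced attrition the plan requires no missing-not-at-random sensitivity analysis for the maternal substance-use outcomes, and the result of the promised test leads nowhere. The gap applies to every outcome, but matters most for substance use.

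The size is illustrative only. At 15/25/35% loss, an odds ratio of 3 in one arm only gives about 1.9/3.3/4.8 points, each below one standard error, and the 5% error rate becomes about 6/8/10%. With the same link in both arms the bias is 0. Every rate, odds ratio and variance is an assumption, as is 1:1 allocation. At the extreme of the wider inputs the bias reaches 7.2 points; the standard error was not recomputed for those inputs.

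A reader might infer that the treatment comparison will be biased, or biased in favor of Healthy Home. The documents support neither: the size and direction of any bias cannot be derived from them, and it may be nil.

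**What to change.** Remove the differential-attrition condition in 4.12. Whatever the attrition balance, run one pre-specified sensitivity analysis for the two substance-use outcomes already named in 4.4 (Addiction Severity Index Lite and urine test): an arm-specific delta-adjusted (pattern-mixture) tipping-point analysis over a grid of deltas fixed in advance on each outcome's own scale. For the urine result, the grid can be read directly. With equal loss, the shift in the risk difference is the share lost times the gap between the arms' deltas; for example, 25% lost and a 20-point gap give 0.25 × 20 = 5 points. The attrition models already cited can stay as optional support.

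Replace reliance on a test of non-ignorability with a description of the predictors of missingness by arm. Report urine results missing because the visit was by phone separately from other missing results.

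The cost is a short change of wording, a few more model runs and the work of choosing delta ranges for two differently scaled outcomes before the data are seen. No new data and no new relapse definition are needed. Conclusions may become more cautious.
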